- If the hemostatic effect is incomplete after TStart and before the primary efficacy endpoint at T4, additional amounts of IP may be applied at the TBS up to the maximum allowed volume of 12 mL for subjects greater than or equal to 2 years of age and 6 mL for subjects less than 2 years of age if necessary. It is recommended to remove accumulated blood from the surrounding tissues and the target area to be treated according to normal practice in order to have a dry field prior to application of IP (e.g., by means of suction, sponges or sterile gauzes). These additional applications of IP should be performed via spray or drip application as per the investigator's judgment for soft tissue type and via spray application for parenchymous tissue type. The time of start (TStart2) and end (TEnd2) of IP re-application will be recorded. No additional amounts of IP may be applied beyond the primary efficacy endpoint assessment time point at T4.
- The approximate total amount of IP applied to the TBS and the method(s) of administration (drip or spray) will be documented.
- Subjects in the either treatment group should not receive any alternative hemostatic product or treatment (including application of manual pressure) during the 10-minute observational period, apart from re-application of IP before the primary efficacy endpoint at T4, unless there is Grade 3 or 4 (see Table 7-1) breakthrough bleeding at the TBS that jeopardizes subject safety according to surgeon's judgment, in which case the surgeon may use any other hemostatic measure at his/her discretion (the use of FS Grifols, EVICEL, or other plasma-derived hemostatic agents are not allowed in this case). In this case, the subject will be considered a treatment failure. The alternative treatment applied will be recorded in subject's source documents and eCRF.
- IP can only be applied to the TBS in this study.

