### 7.2.1.3.3 OBSERVATIONAL PERIOD

An observational period of 10 minutes will occur following TStart to determine whether hemostasis has been achieved at the TBS as described in Section 7.2.1.3.2.

- Vital signs (HR, RR [indicate if the subject is or is not under mechanical ventilation when the measure is taken], SBP and DBP, and T) will be recorded at 5 minutes after TStart.
- Confirmation of existing and recording of any new medications, except gaseous
  anesthetics, or changes in medications administered to the subject since the last
  assessment (it includes also any blood products administered to the subject). Use of
  anticoagulants and any neutralizing agent should be also recorded in detail including dose
  and time of administration.

• Assessment of hemostasis.

Hemostasis at the TBS will be assessed by the investigator (surgeon) at T4, T7, and T10. Hemostasis is defined as an absence/cessation of bleeding (Grade 0) at the TBS according to the investigator's (the surgeon's) judgment, so that the surgical closure of the exposed field could begin.

In order to facilitate the observation of hemostasis, investigators should remove any excess of accumulated blood around the TBS area by careful aspiration/suction and/or gentle sponging with the edge of a sterile pad, for instance.

Rebleeding is defined as Grade ≥1 bleeding from the TBS that requires further hemostatic intervention (e.g., manual pressure) after hemostasis is previously achieved at the TBS. If the TBS rebleeds but cessation of rebleeding is again achieved at a later time point, the effective hemostatic time point will be when the cessation of rebleeding happened.

Assessment of AEs.

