3.1.1 Primary Efficacy Variable

The primary efficacy variable is the proportion of subjects achieving hemostasis (binary decision: hemostatic response, Grade $0 = \text{Yes/Grade} \ge 1 = \text{No}$) at the TBS by T_4 without occurrence of rebleeding or reapplication of study treatment after T_4 and until T_{Closure} , and without Grade 3 or Grade 4 bleeding, or use of alternative hemostatic treatment after T_{Start} and until T_{Closure} . Hemostasis is defined as Grade 0 bleeding at the TBS according to the investigator's (surgeon's) judgment, so that the surgical closure of the exposed field could begin. Rebleeding is defined as Grade ≥ 1 bleeding from the TBS requiring further hemostatic intervention (eg, manual pressure) after hemostasis was previously achieved at the TBS.

The primary efficacy endpoint of hemostasis by T₄ is shown below.

	H	emostas	is	Was study	Did the TBS re-bleed	Primary
	ac	chieved'	?a	treatment re-	after the 10 minute	Efficacy
				applied at	observation period and	Endpoint:
				TBS after T ₄	before T _{Closure} , or was	Hemostasis
				and before	alternative hemostatic	by T ₄ ?
				T _{Closure} ? ^b	treatment used at the	
					TBS, or was there Grade	
					3 or Grade 4 bleeding at	
					TBS during the 10-	
					minute observational	
					period and until T _{Closure} ? ^b	
					period and antir Telosure:	
Scenario	T ₄	T ₇	T ₁₀			
Section	14	1 /	110			

1	Yes	Yes	Yes	No	No	Yes
2	No	No a	Yes or at any point	Either Yes or No	Either Yes or No	No
3	Either Yes or No		nt any point	Either Yes or No	Either Yes or No	No
4	Eithe	er Yes o	r No	Yes	Either Yes or No	No
5	Eithe	Either Yes or No		Either Yes or No	Yes	No

Page 9 of 18

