3.1.2.2 Prevalence of Treatment Failures

The following cases will be considered treatment failures:

- Persistent bleeding at the TBS beyond T₄
- Grade 3 or Grade 4 breakthrough bleeding from the TBS that jeopardizes subject safety according to the investigator's judgment at any moment during the 10-minute observational period and until T_{Closure}
- Use of alternative hemostatic treatments or maneuvers (other than the study treatment) at the TBS during the 10-minute observational period and until $T_{Closure}$, or use of study treatment at the TBS beyond T_4 and until $T_{Closure}$
- Rebleeding (Grade ≥1) at the TBS after the assessment of the primary efficacy endpoint at T₄ and until T_{Closure}

In the event of Grade 3 or Grade 4 breakthrough bleeding that jeopardizes subject safety according to the investigator's judgment at the TBS at any moment during the 10-minute observational period and until the completion of the surgical closure by layers of the exposed

^a Any missing to the question will be deemed "No".

^b Any missing to the question will be deemed "Yes".

Grifols Worldwide Operations, Ltd

Page 10 of 18

surgical field, the surgeon may use any other hemostatic measures at his/her discretion if
deemed necessary (use of FS Grifols, EVICEL, or other plasma-derived hemostatic agents
are not allowed in this case). In such a case, the subject will be considered a treatment failure.

The alternative treatment used will be recorded in the subject's source documents and
electronic case report forms (eCRFs).

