In this study, 2 types of applicator devices are used to apply FS Grifols (Fibrijet® device up to 30 November 2019, VistaSealTM Dual Applicator thereafter). A sensitivity analysis for the primary efficacy endpoint using mITT will be performed for the subgroups based on the use of different applicators, to compare FS Grifols-treated subjects with either type of applicator device vs the Evicel treatment group. A subgroup analysis by surgery type will also be provided for this by applicator type analysis.

If any missing hemostatic assessment at TBS at T₄ for a randomized subject occurs, it will be treated as non-hemostasis at TBS at T₄ for the subject in the primary efficacy analysis. A sensitivity analysis with non-missing observational hemostatic assessment at TBS at T₄ will be performed.

Considering that the hemostasis assessment may not be performed exactly at the scheduled time point, as supportive analyses, the primary efficacy variable based on the time window below will also be analyzed using the CMH test. The hemostasis assessment data at each time point will be classified into the appropriate category based on the time window in the table below, according to the elapsed time of hemostasis assessment from the start of initial treatment application (T_{Start}) to T₄, T₇ and T₁₀ time points in eCRF.

Scheduled Event	Time Window (MM:SS)
T ₄ (4 minutes from start of application)	<=4:10
T ₇ (7 minutes from start of application)	>=4:11 to <=7:10
T_{10} (10 minutes from start of application)	>=7:11 to <=10:10

Grifols Worldwide Operations, Ltd

Page 16 of 18

If multiple hemostasis assessments fall within the same time window, for purpose of the supportive analyses, the following two scenarios will be considered:

- (a) the first hemostasis assessment will be selected;
- (b) the last hemostasis assessment will be selected.

If there is no hemostasis assessment within a specific time window, the last hemostasis assessment within the previous time window will be carried forward. If there is no hemostasis assessment within the first time window (\leq =4:10), the hemostasis assessment will be deemed non-hemostasis success at T₄. The hemostasis assessment with the elapsed time from T_{Start} greater than 10 minutes and 10 seconds will be classified into the period that is after the 10-minute observational period and before the T_{Closure}.

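### The SAP 9.1 sensitivity analysis restricted to recorded T4 readings would drop children whose primary endpoint is already a settled failure; the primary analysis is unaffected

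*SAP*

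**What the plan says.** **Missing T4.** In SAP 9.1 the sentence beginning "If any missing hemostatic assessment at TBS at" T4 scores such a child as non-hemostasis in the primary analysis. The next sentence plans "A sensitivity analysis with non-missing observational hemostatic assessment at TBS" at T4. It states no exception.

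**The endpoint.** Under SAP 3.1.1, success needs more than Grade 0 at T4. The course must also be "without Grade 3 or Grade 4 bleeding, or use of alternative hemostatic treatment after" the start of application and up to TClosure, with no rebleeding or reapplication after T4. In the scenario table, three rows give failure whatever T4 shows:
- scenario 3: non-hemostasis at a later reading;
- scenario 4: reapplication after T4;
- scenario 5: late rebleeding, alternative treatment, or Grade 3 or 4 bleeding.

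Footnotes to the table deem a missing hemostasis answer *No* and a missing event answer *Yes*.

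**Rescue.** Protocol 6.1 bars other hemostatic treatment in the 10-minute period unless Grade 3 or 4 breakthrough bleeding endangers the child, "in which case the surgeon may use any other hemostatic measure at his/her discretion". SAP 3.1.2.2 says of such bleeding: "In such a case, the subject will be considered a treatment failure". Both cover the minutes before T4.

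**Who assesses.** Protocol 7.2.1.3.3: "Hemostasis at the TBS will be assessed by the investigator (surgeon) at" T4, T7 and T10. It does not say whether readings stop or continue after rescue.

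**The concern.** A blank T4 field and an unknown endpoint are different things. The surgeon is both the assessor and the person controlling the bleeding, so a T4 grade could go unrecorded in a child rescued early. That child has failed by definition, yet a filter on the T4 field alone takes the child out of the denominator.

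Every child with a blank T4 is a failure in the primary analysis, so the filter can only raise an arm's success rate. For children whose outcome really is unknown, that is the purpose of the check. For known failures it selects on outcome, and the analysis then describes children who reached a T4 reading rather than all treated children.

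This is the only planned analysis that relaxes the rule that a missing T4 is a failure. The time-window analyses in SAP 9.1 score no reading by 4:10 as failure, and the ITT analysis in SAP section 9 scores untreated children as failures. If more known failures are dropped on FS Grifols than on EVICEL, the check leans toward non-inferiority and could be cited as support it does not provide.

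**Working it through.** **Inputs from the documents.** 86 per arm and 80% response in each (SAP 4.3); margin 0.80 on the ratio and the pooled-ratio and SE formulas (SAP 9.1); two-sided 5% level (SAP section 4).

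**Inputs assumed.** The number of known failures with a blank T4, which the documents do not give, and two equal surgery strata of 43 per arm.

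**Step 1: the plan's own figure.** SE of log ratio = √[2(1−p)/(pn)] = √[0.4/(0.8×86)] = 0.0762. Power = Φ(0.2231/0.0762 − 1.96) = Φ(0.97) = 83.3%. Simulating the stratified SAP interval gives 82.7%. Both agree with the stated power of at least 80%, so the sample size is not in question.

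**Step 2: direction.** If proportions rT and rC of the arms are dropped and all are failures, the expected ratio becomes [pT/(1−rT)]/[pC/(1−rC)]. The true ratio is multiplied by (1−rC)/(1−rT), which is 1 when the proportions are equal and above 1 only when rT exceeds rC.

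**Step 3: a borderline result.** With one stratum the SAP formula reduces to SE² = 1/a − 1/m1 + 1/b − 1/m0.
- Known failures kept, 64/86 v 69/86: ratio 0.928; SE² = 0.003997 + 0.002865 = 0.006862, SE = 0.0828; lower limit = exp(−0.0752 − 0.1624) = 0.789. Margin not cleared.
- Two FS Grifols known failures dropped, 64/84 v 69/86: ratio 0.950; SE² = 0.003720 + 0.002865 = 0.006585, SE = 0.0811; lower limit = exp(−0.0517 − 0.1590) = 0.810. Margin cleared.
- Two EVICEL known failures dropped instead, 64/86 v 69/84: ratio 0.906; SE² = 0.003997 + 0.002588 = 0.006585; lower limit = exp(−0.0987 − 0.1590) = 0.773. The check moves the other way.

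The two-stratum calculation gives the same limits for the first two cases.

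**Step 4: range.** Lower limits with two strata, EVICEL 69/86, dropping from FS Grifols only:

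| FS Grifols | none dropped | 1 | 2 | 5 |
|---|---|---|---|---|
| 69/86 | 0.862 | 0.874 | 0.886 | 0.925 |
| 66/86 | 0.818 | 0.829 | 0.840 | 0.876 |
| 64/86 | 0.789 | 0.799 | 0.810 | 0.845 |
| 60/86 | 0.731 | 0.740 | 0.750 | 0.782 |

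Each dropped child adds about 0.010 to 0.013. The verdict of the check changes only near the margin. With 69/86 in both arms and two dropped from each, the ratio stays 1.00 and the limit moves from 0.862 to 0.869.

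**Step 5: at the margin.** With true rates of 64% v 80% (ratio 0.80), 200,000 simulated trials put the lower limit above 0.8 in 2.9% when everyone is kept. The restricted analysis gives 3.6% with 1% v 0% dropped, 6.1% with 5% v 2%, 17.6% with 10% v 2%, and 3.1% with 5% in both arms. All these dropping rates are assumptions.

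**The case against.** **No decision rests on this analysis.** This stands. A reader might take the percentages in Step 5 as false-positive rates for the trial. The documents do not support that: the non-inferiority rule in SAP 9.1 and Protocol 9.1.2 applies to the primary analysis, which counts these children as failures. In 14.8 of the 17.6 percentage points above, the primary analysis has already missed the margin.

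**The premise may not occur.** This stands in part. It needs severe bleeding or another failure event together with a blank T4. Children enter with Grade 1 or 2 bleeding only, T4 is scheduled for all, and a surgeon treating breakthrough bleeding can see that hemostasis is absent. If T4 is always recorded, the effect is nil. But nothing in either document guarantees a T4 entry after rescue, and the SAP itself provides for missing T4 readings.

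**The larger rates look high.** This stands. Protocol 2.3.1 reports total treatment failure on FS Grifols of 7.2% in parenchymous and 17.2% in soft tissue surgery. Early rescue with a blank T4 at 5% would be about 69% of the first (5/7.2) or 29% of the second (5/17.2); 10% exceeds the first altogether.

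**These failures are counted elsewhere.** True: treatment failures are a secondary endpoint with a CMH test (SAP 9.2). That limits the harm but does not make this check sound.

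**The sentence never says that known failures are excluded.** It is brief, but restriction to recorded T4 is its natural reading, and no text keeps known failures in.

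**If every blank T4 is a known failure, the corrected analysis equals the primary one.** Correct, and appropriate: nothing is then unknown, so there is nothing to test.

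**Conclusion.** The point holds as a flaw in one robustness check. Read as written, SAP 9.1 would discard children whose composite endpoint is already a failure under SAP 3.1.1. Early rescue with a blank T4 is one case; a blank T4 followed by recorded bleeding at T7 or T10 is another.

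The primary analysis, the sample size and the non-inferiority decision are untouched. The size of the effect cannot be fixed from the documents. It is nil if T4 is recorded in all such children, and the ratio is unbiased if equal proportions are dropped, although both success rates then rise. Where the numbers differ, each FS Grifols known failure dropped adds roughly 0.01 to the lower limit, so two could carry a result such as 64/86 v 69/86 across 0.80 in this check alone.

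A reader might infer that the plan favours FS Grifols. The documents do not support that either: they give no early-rescue rate for either arm, and an excess on EVICEL would push the check the other way. The wording should be corrected before unblinding so that the check tests what it is meant to test.

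**What to change.** Replace the sentence in SAP 9.1 with:

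> A sensitivity analysis will exclude only subjects with a missing T4 assessment whose primary endpoint is not otherwise determined. Subjects with a missing T4 assessment and any recorded failure component under the Section 3.1.1 table (non-hemostasis recorded at T7 or T10, Grade 3 or 4 bleeding, alternative hemostatic treatment, rebleeding, or study-treatment reapplication after T4 and before TClosure) remain in the analysis as failures. For this purpose only recorded answers count, not answers deemed *No* or *Yes* because they are missing.

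The last sentence is needed because the table footnotes turn missing answers into failures. Applied here, they would classify children with no information as known failures and defeat the check.

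Also tabulate missing T4 assessments by arm, with and without a recorded failure component, so that a reader can see how much the check depends on them.

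Cost: one SAP sentence, one small table and a little programming. The items already feed the Section 3.1.1 table, so nothing new is collected. The sensitivity result may be slightly less favourable than under the present wording.

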9.1 Primary Efficacy Analysis

The primary efficacy variable is the proportion of subjects achieving hemostasis by T₄ based on its nominal scheduled time point at TBS.

Assuming that T is the response rate for the FS Grifols treatment group, C is the response rate for the EVICEL group (control group), M is the pre-specified non-inferiority margin.

The null hypothesis (H_0) is: Risk Ratio $(T/C) \le 1$ -M and

the alternative hypothesis (H₁) is: Risk Ratio (T/C) \geq 1-M,

where 1-M is 0.8.

The primary efficacy endpoint will be analyzed using Cochran-Mantel-Haenszel (CMH) test stratified by type of surgery (i.e., parenchymous surface of liver versus soft tissue surgery). The ratio of proportion (RR_{pooled}) of subjects meeting the primary efficacy endpoint in the two treatment groups (FS Grifols relative to EVICEL) and its two-sided asymptotic 95% confidence interval (CI) will be provided:

$$RR_{pooled} = \frac{\sum_{i} a_{i} * m_{0i} / N_{i}}{\sum_{i} b_{i} * m_{1i} / N_{i}}$$

The asymptotic 95% confidence interval of RR_{pooled} is calculated as:

Lower limit =
$$\exp\{\ln(RR_{pooled}) - Z_{\alpha/2} * SE\}$$

Upper limit =
$$\exp\{\ln(RR_{pooled}) + Z_{\alpha/2} * SE\}$$

Where the standard error (SE) is calculated as:

Grifols Worldwide Operations, Ltd Page 15 of 18
$$SE = \sqrt{\frac{\sum_{i} (n_{1i} * m_{1i} * m_{0i} - a_{i} * b_{i} * N_{i}) / N_{i}^{2}}{(\sum_{i} a_{i} * m_{0i} / N_{i})(\sum_{i} b_{i} * m_{1i} / N_{i})}}$$

where a_i , b_i , c_i , d_i , n_{1i} , n_{0i} , m_{1i} , m_{0i} , and N_i are the number of subjects defined in following table; i = 1 or 2 according to different types of surgeries (i.e., parenchymous surface of liver or soft tissue surgery).

		FS Grifols	EVICEL	Total
Hemostasis	Yes	$a_{\rm i}$	b_{i}	n_{1i}
achieved?	No	c_{i}	d_i	n_{0i}
Total		m_{1i}	m _{0i}	Ni

The non-inferiority will be deemed to have been demonstrated if the lower limit of the 95% CI exceeds 0.8. After the non-inferiority of FS Grifols to EVICEL is established, its superiority may be additionally claimed if the 95% CI for the ratio is entirely above 1.

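### In the supportive actual-time analysis, a late T7 reading lets the window rules drop a recorded Grade ≥1 reading and score a success that SAP 3.1.1 scores as a failure

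*SAP*

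**What the plan says.** The primary analysis uses scheduled times (SAP 9.1): "The primary efficacy variable is the proportion of subjects achieving hemostasis by T₄ based on its nominal scheduled time point at TBS". Because readings may be off schedule, the SAP adds a second look: "as supportive analyses, the primary efficacy variable based on the time window below will also be analyzed using the CMH test". The windows are up to 4:10 for T4, 4:11 to 7:10 for T7 and 7:11 to 10:10 for T10. A later reading is assigned to the period between the 10-minute observation and TClosure.

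Three rules then apply:

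- Several readings in one window: "for purpose of the supportive analyses, the following two scenarios will be considered". In (a), "the first hemostasis assessment will be selected"; in (b), "the last hemostasis assessment will be selected".
- Empty later window: "If there is no hemostasis assessment within a specific time window, the last hemostasis assessment within the previous time window will be carried forward".
- Empty first window: "the hemostasis assessment will be deemed non-hemostasis success at T₄".

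SAP 3.1.1 defines the endpoint as hemostasis by T4 "without occurrence of rebleeding or reapplication of study treatment after" T4 up to TClosure, with no Grade 3 or 4 bleeding and no alternative treatment from TStart. In its scenario table, the only success row needs Yes at T4, T7 and T10 and No in both event columns. SAP 3.1, SAP 4.1 and footnote a to that table treat a missing hemostasis reading as No.

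**The concern.** The supportive analysis exists to show whether the result depends on reading times, so it should differ from the nominal analysis only through timing. As written, it can also drop a recorded Grade ≥1 reading, because no rule lets such a reading override a Grade 0 reading in the same window or a carried Yes.

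Within the 10 minutes, the T7 and T10 readings are the table's only detector of mild or moderate bleeding managed per protocol. The table's rebleed question starts after that period, and Protocol 6.1 and 6.3 restrict in-period treatment. What is at stake is the use of this analysis as evidence of robustness: agreement of (a) and (b) could be cited as reassurance that it does not provide.

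**Working it through.** **The plan's own figure.** The documents give no rate of late readings. Their related figure is power of at least 80% with 86 per arm, 80% vs 80% and a ratio margin of 0.8 (SAP 4.3). On the log-ratio scale, SE = √(2 × 0.2 / (0.8 × 86)) = 0.0762. Power = Φ(0.2231/0.0762 − 1.96) = 83.3%. The figure is reproduced, and this point does not change it.

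**Mechanism.** Take T4 on time, T7 a few seconds past its window and T10 on time, with no event recorded in the table's other columns.

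| Readings | T4 window | T7 window | T10 window (a) / (b) | Score (a) | Score (b) | SAP 3.1.1 |
|---|---|---|---|---|---|---|
| Yes 4:05, Yes 7:15, No 10:05 | Yes | Yes (carried) | Yes / No | success | failure | failure |
| Yes 4:05, No 7:15, Yes 10:05 | Yes | Yes (carried) | No / Yes | failure | success | failure |

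All combinations of on-time or late and Grade 0 or Grade ≥1 for the three scheduled readings were enumerated. These two are the only ones in which first/last selection turns a recorded Grade ≥1 into a success, and neither does so under both rules. If T4 is late, the first window is empty and the subject fails.

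This counts a Grade ≥1 reading after 10:10 as a failure in the pre-closure period. If it were not counted, carry-forward into the empty T10 window would give a success under both rules after Grade 0 readings at an on-time T4 and at T7.

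**Missing readings.** If T7 or T10 was never taken after a T4 Yes and no Grade ≥1 was read, carry-forward gives a success under both (a) and (b). The missing-is-No rule gives a failure.

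**Size.** Let J be the joint probability of T4 ≤4:10, T7 ≥7:11 and T10 ≤10:10. Let r be the rate of the one pattern that a given rule misses. With 80% success in each arm when all readings count, the ratio is multiplied by (0.8 + J·r_FS)/(0.8 + J·r_EV). Assume Grade ≥1 readings of 8% (FS Grifols) vs 2% (EVICEL), split evenly, so r = 4% vs 1%:

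| J | Factor | Inflation | Added successes per 86 (FS / EVICEL) |
|---|---|---|---|
| 10% | 0.804/0.801 | 0.4% | 0.34 / 0.09 |
| 20% | 0.808/0.802 | 0.7% | 0.69 / 0.17 |
| 50% | 0.820/0.805 | 1.9% | 1.72 / 0.43 |

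With equal rates, the factor is 1.

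**Can both rules err together?** With one stratum, the SAP 9.1 interval reduces to lower limit = (a/b) × exp(−1.96 × √(1/a + 1/b − 2/86)). Assume all-readings counts of 64/86 (FS Grifols) and 69/86 (EVICEL):

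- All readings: 0.9275 × exp(−1.96 × 0.0828) = 0.789, below 0.8.
- If two of the FS Grifols failures have the timing above, one of each pattern, each rule rescues one. Both then give 65/86: 0.9420 × exp(−1.96 × 0.0814) = 0.803, above 0.8.

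So the rules can agree on the wrong side of the margin. The counts were chosen to lie near it. From 69/86 vs 69/86 the lower limit is 0.862. It falls to 0.847, 0.833, 0.818, 0.803 and 0.789 as 1 to 5 FS Grifols successes become failures.

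**The case against.** The strongest reply has four parts.

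- **Treated bleeding is still caught.** Re-application after T4, alternative treatment (including manual pressure), Grade 3 or 4 bleeding and later rebleeding have their own columns. This stands. A reader might infer that an observed rebleed is scored as success, but SAP 3.1.1 calls bleeding a rebleed only if it requires further intervention. What slips through is a Grade 1 or 2 reading with no such event recorded. That is more plausible for Yes/No/Yes than for Yes/Yes/No, where bleeding at T10 must go untreated to closure. SAP 3.1.1 still fails both patterns.
- **The two rules bracket the result.** This holds for each subject, since a subject rescued by one rule fails under the other. It does not hold for the success counts, because the rules miss different subjects.
- **The effect is small and its net direction is open.** This stands. The timing condition is joint, the imbalance is assumed, and setting T4 readings after 4:10 to failure removes successes. Giving one rule the full 8% vs 2% yields 0.7%, 1.5% and 3.7%, but only if every such reading has the one pattern that rule misses; the other rule then gains nothing.
- **The analysis is only supportive.** This stands and limits the importance of the point.

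**Conclusion.** The scoring error holds for the supportive actual-time analysis. Under the stated timing, rule (a) or rule (b) can count as a success a subject whom SAP 3.1.1 fails, and through this route neither count can fall below the all-readings count. Agreement of (a) and (b) is therefore not evidence of robustness.

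A reader might infer that the trial's non-inferiority conclusion is at risk or biased toward FS Grifols. The documents do not support that: the decision rests on nominal times, and the ratio is inflated only if the missed pattern is more frequent with FS Grifols. The size is probably small, about 0.4% to 1.9% on the ratio in the illustration. That range rests on assumed values for the joint timing probability (10% to 50%), the reading rates (8% vs 2%) and the even split, and on there being only the three scheduled readings. It is worth correcting because the plan contradicts its own endpoint definition and the correction is cheap.

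**What to change.** In SAP 9.1:

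1. State that any recorded Grade ≥1 reading after T4 and up to TClosure makes the subject a failure in the supportive analysis, whichever window it falls in and whichever reading is selected or carried forward.
2. Limit carry-forward to a window left empty because its scheduled reading was taken but fell in another window. Score a reading that was never taken as No, in line with SAP 3.1, SAP 4.1 and footnote a to the scenario table.
3. Tabulate by arm the readings moved to another window, including T4 readings after 4:10 that are set to failure.

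The cost is a sentence or two of SAP text, a few lines of code and slightly lower supportive success rates. Sample size and the primary analysis do not change.
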